**List of Abbreviations**

Abbreviation	Description
AUC 0-t	The area under the plasma concentration-time curve, from time 0 (time of dosing) to the last time point with measurable analyte concentration, calculated by the log down, linear up trapezoidal method.
AE	Adverse Event
ATC	Anatomical Therapeutic Class
AUC 0-inf	The area under the plasma concentration-time curve from time 0 extrapolated to infinity. AUC 0-inf is calculated as the sum of AUC 0-t plus the ratio of the last measurable plasma concentration to the elimination rate constant ( $k_{el}$ ).
AUC 0-8	The area under the plasma concentration-time curve, from time 0 (time of dosing) to the 8 hours concentration, calculated by the log down, linear up trapezoidal method.
BLQ	Below the quantitation limit
CAP	Community-Acquired Pneumonia
CBC	Complete Blood Count
C max	Maximum observed concentration
C min	Minimum observed concentration over the dosing interval.
CL/F	Apparent clearance calculated as Dose/AUC 0-inf .
CS	Clinically Significant
CSR	Clinical Study Report
CV	Coefficient of variation
DLT	Dose Limiting Toxicity
DN_AUC 0-inf	Dose-normalized AUC 0-inf , calculated as AUC 0-inf divided by dose.
DN_AUC 0-t	Dose-normalized AUC 0-t , calculated as AUC 0-t divided by dose.
DN_AUC 0-8	Dose-normalized AUC 0-8 , calculated as AUC 0-8 divided by dose.
DN_C max	Dose-normalized C max , calculated as C max divided by dose.
EKG	Electrocardiogram
eCRF	Electronic Case Report Form
EOS	End of Study
GCP	Good Clinical Practice
geo CV	Geometric Coefficient of Variation
HIV	Human Immunodeficiency Virus
ITT	Intention-to-treat
IV	Intravenous
IWRS	Interactive web response system
k el	Apparent terminal elimination rate constant, calculated by linear regression of the terminal linear portion of the log concentration vs. time curve.
LLQ	Lower Limit of Quantification
MAD	Multiple-Ascending Dose
MedDRA	Medical Dictionary for Regulatory Activities
MMSE	Mini-Mental State Exam
N/A	Not Applicable
NCS	Not Clinically Significant

Abbreviation	Description
NK	Not Known
PE	Physical Examination
PI	Principal Investigator
PK	Pharmacokinetic
PP	Per Protocol
PSI	Pneumonia Severity Index
PT	Preferred Term
rhu-pGSN	Recombinant human plasma Gelsolin
SAE	Serious Adverse Event

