## 9. PHARMACOKINETICS (PK)

All PK summary tables and figures will be based on the PK Population. All listings will be based on the Safety Population (Actual Treatment). All analyses will be done by treatment group.

For the 1 dose in the SD arm and the first 2 doses in the MAD arms, blood will be drawn within 30 minutes pre-dose, and 5-10 minutes after the end of administration, as well as 2, 8, 12 and/or 16, and 24 hours after the end of administration ( $\pm$  30 minutes) for analysis. Identical PK sampling is encouraged on Day 3 where feasible (but not required) in the multiple-dose arms.

In this section (section 9):

- The rhu-pGSN treatment group will be referred to the Active treatment group.
- Exogenous pGSN concentrations will be referred to as rhu-pGSN concentrations.
- Endogenous pGSN + Exogenous pGSN (total) will be referred to as pGSN

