### 9.1 Definition of variables

The following PK parameters for pGSN will be estimated For Day 1(SD/MAD), Day 2 (MAD) and Day 3 (MAD). PK Parameters will only be calculated for the Active (rhu-pGSN) treatment group. No PK parameters will be calculated for the Placebo treatment group:

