#### **Day 1: SD/MAD & Day 2/3: MAD**

AUC 0-t	The area under the plasma concentration-time curve, from time 0 (time of dosing) to the last time point (24 hours) with measurable analyte concentration, calculated by the log down, linear up trapezoidal method.  AUC 0-t will additionally be calculated for the estimated rhu-pGSN profile for both the change from pre-dose on each study day and the double-delta method.
AUC 0-8	The area under the plasma concentration-time curve, from time 0 (time of dosing) to the 8 hours concentration, calculated by the log down, linear up trapezoidal method.  AUC 0-8 will additionally be calculated for the estimated rhu-pGSN profile for both the change from pre-dose on each study day and the double-delta method.
AUC 0-inf	The area under the plasma concentration-time curve from time 0 extrapolated to infinity. AUC 0-inf is calculated as the sum of AUC 0-t plus the ratio of the last measurable plasma concentration to the elimination rate constant ( $k_{el}$ ).
C max	Maximum observed concentration.  C max will additionally be calculated for the estimated rhu-pGSN profile for both the change from pre-dose on each study day and the double-delta method.
T max	Time to maximum observed drug concentration. If the maximum value occurs at more than one time point, T max is defined as the first time point with this value.

$k_{el}$	Apparent terminal elimination rate constant calculated by linear regression of the terminal linear portion of the log concentration vs. time curve.
$t_{1/2}$	Apparent elimination half-life, calculated as $\ln(2)/k_{el}$
%AUC ext	Percentage of the extrapolated area under the plasma concentration-time curve, calculated as $100\% * [AUC_{0-inf} - AUC_{0-t}] / AUC_{0-inf}$
$C_L/F$	Apparent clearance calculated as $Dose/AUC_{0-inf}$ .
$V_z/F$	Apparent volume of distribution at the terminal phase, calculated as $Dose / (k_{el} \times AUC_{0-inf})$ .
DN_C max	Dose-normalized C max , calculated as C max divided by dose DN_C max will additionally be calculated for the estimated rhu-pGSN profile for both the change from pre-dose day 1 and the double-delta method..
DN_AUC 0-inf	Dose-normalized AUC 0-inf , calculated as AUC 0-inf divided by dose

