Minimum	x.x	x.x	x.x	x.x
Median	x	x	x	x
Maximum	x	x	x	x
CV%	x.x	x.x	x.x	x.x
GeoMean	x.x	x.x	x.x	x.x
GeoCV%	x.x	x.x	x.x	x.x
C max (unit)				
n	x	x	x	x
Mean	x.x	x.x	x.x	x.x
SD	x.x	x.x	x.x	x.x
Minimum	x.x	x.x	x.x	x.x
Median	x	x	x	x
Maximum	x	x	x	x
CV%	x.x	x.x	x.x	x.x
GeoMean	x.x	x.x	x.x	x.x
GeoCV%	x.x	x.x	x.x	x.x

SD: Standard Deviation; GeoMean: Geometric Mean; GeoCV%: Geometric CV%

Clinical cut-off date: DDMMYYYY  
 Program: filepath\_name, Output: filepath\_name (version x.x) Created: DDMMYYYY HH:MM

Programming Note: Repeat for all PK parameters.

Table 14.2.2.3 Day 3: Summary of Plasma pGSN PK Parameters  
 Protocol: BTI-201  
 PK Population

Parameter (unit)	MAD rhu-pGSN 6 mg/kg (N=xx)	MAD rhu-pGSN 12 mg/kg (N=xx)	MAD rhu-pGSN 24 mg/kg (N=xx)	Placebo (N=xx)
AUC 0-t (unit)				
n	x	x	x	x
Mean	x.x	x.x	x.x	x.x
SD	x.x	x.x	x.x	x.x
Minimum	x.x	x.x	x.x	x.x
Median	x	x	x	x
Maximum	x	x	x	x
CV%	x.x	x.x	x.x	x.x
GeoMean	x.x	x.x	x.x	x.x
GeoCV%	x.x	x.x	x.x	x.x
C max (unit)				
n	x	x	x	x
Mean	x.x	x.x	x.x	x.x
SD	x.x	x.x	x.x	x.x
Minimum	x.x	x.x	x.x	x.x
Median	x	x	x	x
Maximum	x	x	x	x
CV%	x.x	x.x	x.x	x.x
GeoMean	x.x	x.x	x.x	x.x
GeoCV%	x.x	x.x	x.x	x.x

SD: Standard Deviation; GeoMean: Geometric Mean; GeoCV%: Geometric CV%

Clinical cut-off date: DDMMYYYY  
 Program: filepath\_name, Output: filepath\_name (version x.x) Created: DDMMYYYY HH:MM

Programming Note: Repeat for all PK parameters.

Table 14.2.3.1 Day 1: Summary of Estimated Plasma rhu-pGSN PK Parameters  
 Protocol: BTI-201  
 PK Population

	SD/MAD	MAD	MAD
	rhu-pGSN 6 mg/kg (N=xx)	rhu-pGSN 12 mg/kg (N=xx)	rhu-pGSN 24 mg/kg (N=xx)

Parameter (unit)	Change from Pre-Injection		Double Delta Analysis		Change from Pre-Injection		Double Delta Analysis		Change from Pre-Injection		Double Delta Analysis	
	Pre-Injection	Double Delta Analysis	Pre-Injection	Double Delta Analysis	Pre-Injection	Double Delta Analysis	Pre-Injection	Double Delta Analysis	Pre-Injection	Double Delta Analysis	Pre-Injection	Double Delta Analysis
AUC 0-t (unit)	x	x	x	x	x	x	x	x	x	x	x	x
Mean	x.x	x.x	x.x	x.x	x.x	x.x	x.x	x.x	x.x	x.x	x.x	x.x
SD	x.x	x.x	x.x	x.x	x.x	x.x	x.x	x.x	x.x	x.x	x.x	x.x
Minimum	x.x	x.x	x.x	x.x	x.x	x.x	x.x	x.x	x.x	x.x	x.x	x.x
Median	x	x	x	x	x	x	x	x	x	x	x	x
Maximum	x	x	x	x	x	x	x	x	x	x	x	x
CV%	x.x	x.x	x.x	x.x	x.x	x.x	x.x	x.x	x.x	x.x	x.x	x.x
n	x	x	x	x	x	x	x	x	x	x	x	x
Mean	x.x	x.x	x.x	x.x	x.x	x.x	x.x	x.x	x.x	x.x	x.x	x.x
SD	x.x	x.x	x.x	x.x	x.x	x.x	x.x	x.x	x.x	x.x	x.x	x.x

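### SAP 9.1 applies single-dose formulas for AUC0-inf, CL/F, Vz/F and DN_AUC0-inf to MAD Days 2 and 3, so those values cannot be interpreted and their change across days is not a change in kinetics

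*SAP*

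**What the plan says.** SAP 9.1 opens with "The following PK parameters for pGSN will be estimated For Day 1(SD/MAD), Day 2 (MAD) and Day 3 (MAD") and then gives a single list under one heading that covers Day 1 for both parts and Days 2 and 3 for MAD. The formulas do not change by day:

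- AUC0-inf is AUC0-t "plus the ratio of the last measurable plasma concentration to the elimination rate constant".
- CL/F is defined as "Apparent clearance calculated as Dose/AUC 0-inf" (same formula in the abbreviation list and in 9.1).
- Vz/F, "Apparent volume of distribution at the terminal phase", is dose divided by the product of kel and AUC0-inf.
- DN_AUC0-inf is "calculated as AUC 0-inf divided by dose".

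The analyte is the total protein: "Endogenous pGSN + Exogenous pGSN (total) will be referred to as pGSN" (SAP section 9). SAP 9.2 also defines pre-dose-corrected and double-delta profiles, but only AUC0-t, AUC0-8, Cmax and their dose-normalised forms are computed from them.

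MAD subjects receive three doses at 24 h intervals (protocol Table 6, footnote d). The shells for the Day 2 and Day 3 parameter tables (14.2.2.2 and 14.2.2.3) carry the note "Programming Note: Repeat for all PK parameters", and Listing 16.2.6.3.2, titled by day, has columns for all four parameters.

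**The concern.** Dose divided by AUC0-inf equals clearance only when the area comes from that dose alone, which holds after a first dose. The area from the Day 2 dose to infinity also contains the tail of the Day 1 dose, and the Day 3 area contains two tails. The numerator stays at one dose. The same error passes into Vz/F and, inverted, into DN_AUC0-inf.

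The secondary objective is the PK profile after single or multiple doses, and these parameters will be tabulated by day. If clearance and volume differ between the Day 1, Day 2 and Day 3 tables, a reader will naturally see time-dependent kinetics. The formulas produce such differences even when the kinetics are constant.

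**Working it through.** The documents state no figure on this point, so there is none to reproduce.

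**Inputs.** Dosing interval 24 h, three doses, 6, 12 or 24 mg/kg (protocol 6.3, Table 6). Endogenous pGSN 200-300 mg/L in health, lower in illness (protocol 4.3); 100-300 mg/L is used below. No human plasma half-life is given. The only half-life, 10-16 h, is for radioactivity in animal lung (protocol 4.4.1) and is not a plasma value. Half-life and volume (0.05 L/kg) are therefore assumptions.

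**Step 1: exogenous drug alone, linear kinetics.** Let r = exp(-kel x 24 h). By superposition, AUC0-inf after dose n is (Dose/CL) x (1 + r + ... + r^(n-1)). Reported CL/F is then CL/(1+r) on Day 2 and CL/(1+r+r²) on Day 3.

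| Half-life | r | Day 2 factor | Day 3 factor | CL/F low by, Day 2/Day 3 |
|---|---|---|---|---|
| 4 h | 0.0156 | 0.985 | 0.984 | 1.5% / 1.6% |
| 8 h | 0.125 | 0.889 | 0.877 | 11% / 12% |
| 12 h | 0.25 | 0.800 | 0.762 | 20% / 24% |
| 24 h | 0.5 | 0.667 | 0.571 | 33% / 43% |

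Vz/F is low by the same factors. DN_AUC0-inf is high by the reciprocals: 1.25 and 1.31 at 12 h, 1.5 and 1.75 at 24 h.

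**Step 2: total pGSN, as the SAP specifies.** Total pGSN was taken as exogenous drug plus a constant endogenous level. The SAP rules were applied: linear-up/log-down area, kel from the last three points, AUC0-t plus Clast/kel. The dose was treated as a bolus, with samples at 5-10 min and 2, 8, 12 and 24 h. At a 12 h half-life, Day 2/Day 1 CL/F is:

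| Dose | 100 mg/L | 200 mg/L | 300 mg/L |
|---|---|---|---|
| 6 mg/kg | 1.02 | 1.10 | 1.13 |
| 12 mg/kg | 0.94 | 1.02 | 1.06 |
| 24 mg/kg | 0.88 | 0.94 | 0.99 |

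Step 1 gives 0.80 in every cell. Two cells show why the direction changes (areas in mg·h/L):

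- 24 mg/kg, 100 mg/L: Dose/V = 24/0.05 = 480 mg/L. On Day 1, Clast = 480 x 0.25 + 100 = 220, kel = 0.0374 and AUC0-inf = 8,669 + 5,883 = 14,552. On Day 2, Clast = 600 x 0.25 + 100 = 250, kel = 0.0402 and AUC0-inf = 10,230 + 6,219 = 16,449. The CL/F ratio is 14,552/16,449 = 0.88.
- 6 mg/kg, 300 mg/L: Dose/V = 120 mg/L. On Day 1, Clast = 330, kel = 0.0079 and AUC0-inf = 8,781 + 41,797 = 50,578. On Day 2, Clast = 337.5, kel = 0.0095 and AUC0-inf = 9,176 + 35,422 = 44,598. The ratio is 50,578/44,598 = 1.13.

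Residual drug raises the observed area, but it also steepens the fitted slope on a flat background and so shrinks the extrapolated area. Which effect wins depends on the endogenous level relative to Dose/V. The sign changes at about 0.67 of Dose/V for a 12 h half-life (0.49 at 8 h, 0.94 at 24 h).

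Over half-lives of 8-24 h at the same volume, Day 2/Day 1 CL/F ran from about 0.77 to 1.20, and Vz/F fell throughout. If the endogenous level instead rises from 100 to 200 mg/L over 72 h, the CL/F ratio ran from 0.76 to 1.32.

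**Step 3: Day 1.** Under the constant-baseline assumptions, Day 1 CL/F on total pGSN is only about 3% to 62% of true exogenous clearance. This is a separate and usually larger error.

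**The case against.** A reader might infer that the planned tables will show clearance falling by a fifth or more with repeat dosing. The documents do not support that. The Step 1 percentages describe exogenous drug, and the SAP computes no AUC0-inf or CL/F on a corrected profile. On total pGSN the trend can go either way, and at a half-life near 4 h the residual-drug component is negligible.

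The other objections are these:

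- AUCinf is a protocol secondary endpoint (5.2.2), and protocol 11.4.3 samples for it after the first two MAD doses. Removing it on Day 2 departs from the protocol, while SAP section 15 declares no planned changes. This stands and shapes the fix. It does not protect CL/F, Vz/F or DN_AUC0-inf, which the protocol does not name.
- AUC0-t to 24 h, Cmax and pre-dose concentrations by day are already planned. This stands: only accumulation ratios are new.
- PK is descriptive, there are six active subjects per cohort, Day 3 sampling is optional, and escalation rests on Day 7 safety review. This stands too. No passage ties a dose decision to CL/F, so harm to regimen choice is possible but not shown.
- The endogenous background is the larger error. That is correct in the scenarios run, but removing it would leave the residual-drug error of Step 1 in place.

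None of these makes dose over AUC0-inf a clearance on Day 2 or Day 3.

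**Conclusion.** The point holds as a defect of definition. On MAD Days 2 and 3, AUC0-inf, CL/F, Vz/F and DN_AUC0-inf mix several doses with a one-dose formula, and no correction in the SAP reaches them. They should not be read as clearance, volume or single-dose exposure, and differences across days should not be read as changes in kinetics.

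The size is known only conditionally. For exogenous drug with linear kinetics it runs from about 2% at a 4 h half-life to 33% (Day 2) and 43% (Day 3) at 24 h. For total pGSN no direction can be claimed for CL/F. Because the sign depends on dose and endogenous level, cohorts with identical kinetics could show opposite trends. Half-life, volume and the endogenous course are assumptions throughout.

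**What to change.** 1. In SAP 9.1, restrict AUC0-inf, %AUCext, CL/F, Vz/F and DN_AUC0-inf to Day 1.
2. Because the protocol names AUCinf for the first two MAD doses, declare the Day 2 change in SAP section 15. Alternatively, keep Day 2 AUC0-inf with a label that it includes residual drug and is not used for CL/F or Vz/F.
3. For Days 2 and 3, rely on the planned AUC0-t (24 h), Cmax and pre-dose concentrations. Add within-subject accumulation ratios for AUC0-24 and Cmax: Day 2/Day 1, and Day 3/Day 1 where Day 3 was sampled. State which profile they use. The day-specific pre-dose subtraction in 9.2 removes the residual drug that an accumulation ratio is meant to show, and endogenous protein pulls a ratio on total pGSN towards 1.
4. Do not substitute Dose/AUC0-24 as clearance. For exogenous drug it is 1/(1-r^n) times true CL on Day n, which at a 24 h half-life is 2.00, 1.33 and 1.14 on Days 1 to 3.
5. Limit the repeat-all note for Tables 14.2.2.2 and 14.2.2.3, and the Day 2-3 pages of Listing 16.2.6.3.2, to match.

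The cost is SAP and shell wording plus one declared change; no new samples are needed. This does not make Day 1 CL/F and Vz/F valid: they still need a separate correction for endogenous pGSN.

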#### **Day 1: SD/MAD & Day 2/3: MAD**

AUC 0-t	The area under the plasma concentration-time curve, from time 0 (time of dosing) to the last time point (24 hours) with measurable analyte concentration, calculated by the log down, linear up trapezoidal method.  AUC 0-t will additionally be calculated for the estimated rhu-pGSN profile for both the change from pre-dose on each study day and the double-delta method.
AUC 0-8	The area under the plasma concentration-time curve, from time 0 (time of dosing) to the 8 hours concentration, calculated by the log down, linear up trapezoidal method.  AUC 0-8 will additionally be calculated for the estimated rhu-pGSN profile for both the change from pre-dose on each study day and the double-delta method.
AUC 0-inf	The area under the plasma concentration-time curve from time 0 extrapolated to infinity. AUC 0-inf is calculated as the sum of AUC 0-t plus the ratio of the last measurable plasma concentration to the elimination rate constant ( $k_{el}$ ).
C max	Maximum observed concentration.  C max will additionally be calculated for the estimated rhu-pGSN profile for both the change from pre-dose on each study day and the double-delta method.
T max	Time to maximum observed drug concentration. If the maximum value occurs at more than one time point, T max is defined as the first time point with this value.

$k_{el}$	Apparent terminal elimination rate constant calculated by linear regression of the terminal linear portion of the log concentration vs. time curve.
$t_{1/2}$	Apparent elimination half-life, calculated as $\ln(2)/k_{el}$
%AUC ext	Percentage of the extrapolated area under the plasma concentration-time curve, calculated as $100\% * [AUC_{0-inf} - AUC_{0-t}] / AUC_{0-inf}$
$C_L/F$	Apparent clearance calculated as $Dose/AUC_{0-inf}$ .
$V_z/F$	Apparent volume of distribution at the terminal phase, calculated as $Dose / (k_{el} \times AUC_{0-inf})$ .
DN_C max	Dose-normalized C max , calculated as C max divided by dose DN_C max will additionally be calculated for the estimated rhu-pGSN profile for both the change from pre-dose day 1 and the double-delta method..
DN_AUC 0-inf	Dose-normalized AUC 0-inf , calculated as AUC 0-inf divided by dose
DN_AUC 0-t	Dose-normalized AUC 0-t , calculated as AUC 0-t divided by dose DN_AUC 0-t will additionally be calculated for the estimated rhu-pGSN profile for both the change from pre-dose on each study day and the double-delta method.
DN_AUC 0-8	Dose-normalized AUC 0-24 , calculated as AUC 0-24 divided by dose DN_AUC 0-8 will additionally be calculated for the estimated rhu-pGSN profile for both the change from pre-dose on each study day and the double-delta method.

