4.3. Plasma Gelsolin and Treatment of CAP

Plasma gelsolin is a human protein produced and secreted by virtually every cell type, and it circulates at high levels in the blood of healthy individuals. At normal levels of 200-300 mg/L, it is the fourth most abundant protein in the circulation.

The therapeutic protein being developed by BioAegis Therapeutics, Inc. (BioAegis or Sponsor) is recombinant human plasma gelsolin (rhu-pGSN) and was formerly referred to as BG9385. It is identical to the complete natural protein and is comprised of 755 amino acids. The protein, like the natural protein, is non-glycosylated. The protein consists of six repeated domains, which make up three distinct actin binding sites, two that bind globular actin (G-actin) and one that binds filamentous actin (F-actin). Domain 1 plus the first 10 amino acids of domain 2 of gelsolin is the minimal fragment size required for its actin severing activity. Rhu-pGSN contains multiple calcium binding sites that regulate its activity. It is a highly conserved protein, as far back as *Drosophila*.

Plasma gelsolin modulates inflammation while at the same time, boosting the body's ability to clear pathogens. It functions through mechanisms quite distinct from anti-inflammatory agents, which are antagonists of specific mediators or inhibitors of specific enzymes. Plasma gelsolin functions through a pleiotropic mechanism of action, scavenging toxic actin, binding inflammatory mediators and enhancing pathogen clearance. pGSN levels decrease markedly in a variety of clinical conditions such as acute respiratory distress syndrome, sepsis, major trauma, prolonged hyperoxia, malaria, and liver injury. The strength of the correlation between magnitude of decline in pGSN and likelihood of mortality is especially striking (Lee et al, 2006; 2008; 2009; Osborn et al, 2008). Repletion of depressed plasma gelsolin levels with rhu-pGSN is expected to benefit patients through four distinct mechanisms that have been described in the literature:

1. *Sequestration of released actin from sites of damage.* This sequestration causes local depletion of pGSN while leaving large stores of pGSN continuing to circulate in healthy individuals. Modest reduction of systemic pGSN levels is then restored after healing is complete (Haddad et al, 1990; Lee et al, 1992).

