#### Analysis of Estimated rhu-pGSN

This analysis will exclude the placebo treatment group:

- Pre-dose values on each study day will be presented as recorded;
- Pre-dose values on each study day that are BLQ will be set to  $\frac{1}{2}$  LLQ;
- Subsequent BLQ values (post the first quantifiable concentration on each day) will be set to  $\frac{1}{2}$  LLQ.
- Estimated rhu-pGSN concentration  
= concentration on Day z at Time Point y – Day z Pre-dose concentration

Individual estimated rhu-pGSN concentrations will be summarized by nominal sampling time. Geometric summary statistics will not be calculated for estimated rhu-pGSN concentrations, as these values could be lower than or equal to 0.

Estimated Individual (for each subject) and mean estimated plasma rhu-pGSN concentration over time will be displayed graphically in linear plots of estimated rhu-pGSN concentration versus time. The actual collection time will be used for individual estimated plasma rhu-pGSN concentration curve and the nominal time will be used for plot of mean estimated plasma rhu-pGSN concentration curve.

Estimated plasma concentrations vs. time data will be analyzed using SAS software. Actual collection time will be used in the calculation of plasma PK parameters. The following parameters (including dose normalized parameters) will be calculated for each study day:

- $AUC_{0-t}$
- $AUC_{0-8h}$
- $C_{max}$

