	Maximum	x	x	x	
	CV%	x.x	x.x	x.x	
	BLQ	x (xx.x%)	x (xx.x%)	x (xx.x%)	

SD: Standard Deviation; BLQ: Below Limit of Quantification

Clinical cut-off date: DDMMYYYY

Program: filepath\_name, Output: filepath\_name (version x.x) Created: DDMMYYYY HH:MM

Programming Note: Repeat for all timepoints.

Table 14.2.1.5 Day 2: Summary of Estimated Plasma rhu-pGGSN Concentrations (unit) by Timepoint (continued)  
 Protocol: BTI-201  
 PK Population

Time Point	MAD rhu-pGGSN 24 mg/kg (N=xx)	Actual Value	Change from Pre-Injection	(Change from Pre-Injection) - (Mean Placebo Change from Pre- Injection)	Actual Value	Change from Pre-Injection
Pre-Injection		n x x.x x.x x.x x x x.x x (xx.x%)			x x.x x.x x.x x x x.x x (xx.x%)	
5 to 10 mins post		n Mean SD Minimum Maximum CV% BLQ	x x.x x.x x.x x x x.x x (xx.x%)		x x.x x.x x.x x x x.x x (xx.x%)	x x.x x.x x.x x x x.x x (xx.x%)

SD: Standard Deviation; GeoMean: Geometric Mean; GeoCV%: Geometric CV%; BLQ: Below Limit of Quantification

Clinical cut-off date: DDMMYYYY  
 Program: filepath\_name, Output: filepath\_name (version x.x) Created: DDMMYYYY HH:MM

Programming Note: Repeat for all timepoints.

Table 14.2.1.6 Day 3: Summary of Estimated Plasma rhu-pGSN Concentrations (unit) by Timepoint  
Protocol: BTI-201  
PK Population

Programming Note: Repeat Table 14.2.1.5 for Day 3.

Table 14.2.2.1 Day 1: Summary of Plasma pGSN PK Parameters  
 Protocol: BTI-201  
 PK Population

Parameter (unit)	SD/MAD rhu-pGSN 6 mg/kg (N=xx)	MAD rhu-pGSN 12 mg/kg (N=xx)	MAD rhu-pGSN 24 mg/kg (N=xx)	Placebo (N=xx)
AUC 0-t (unit)				
n	x	x	x	x
Mean	x.x	x.x	x.x	x.x
SD	x.x	x.x	x.x	x.x
Minimum	x.x	x.x	x.x	x.x
Median	x	x	x	x
Maximum	x	x	x	x
CV%	x.x	x.x	x.x	x.x
GeoMean	x.x	x.x	x.x	x.x
GeoCV%	x.x	x.x	x.x	x.x
C max (unit)				
n	x	x	x	x
Mean	x.x	x.x	x.x	x.x
SD	x.x	x.x	x.x	x.x
Minimum	x.x	x.x	x.x	x.x
Median	x	x	x	x
Maximum	x	x	x	x
CV%	x.x	x.x	x.x	x.x
GeoMean	x.x	x.x	x.x	x.x
GeoCV%	x.x	x.x	x.x	x.x

SD: Standard Deviation; GeoMean: Geometric Mean; GeoCV%: Geometric CV%

Clinical cut-off date: DDMMYYYY  
 Program: filepath\_name, Output: filepath\_name (version x.x) Created: DDMMYYYY HH:MM

Programming Note: Repeat for all PK parameters.

Table 14.2.2.2 Day 2: Summary of Plasma pGSN PK Parameters  
 Protocol: BTI-201  
 PK Population

Parameter (unit)	MAD rhu-pGSN 6 mg/kg (N=xx)	MAD rhu-pGSN 12 mg/kg (N=xx)	MAD rhu-pGSN 24 mg/kg (N=xx)	Placebo (N=xx)
AUC 0-t (unit)				
n	x	x	x	x
Mean	x.x	x.x	x.x	x.x
SD	x.x	x.x	x.x	x.x

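### Dose-normalised parameters of total pGSN fall with dose even under proportional kinetics; the SAP does not name the corrected set as the one to read, and DN_AUC0-inf has no corrected version

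*SAP*

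**What the plan says.** SAP Section 9 separates two quantities. Exogenous protein is called rhu-pGSN, and "Endogenous pGSN + Exogenous pGSN (total) will be referred to as pGSN". Section 9.1 then opens with "The following PK parameters for pGSN will be estimated", restricted to the active arms, so each parameter listed there is in the first place a parameter of the total. The DN_Cmax row reads "Dose-normalized C max , calculated as C max divided by dose". The rows for DN_AUC0-t, DN_AUC0-8 and DN_AUC0-inf follow the same pattern, and none subtracts a baseline. Mock Table 14.2.2.1 shows two parameters of total pGSN and adds "Programming Note: Repeat for all PK parameters". Listings 16.2.6.3.x have columns for all four dose-normalised parameters.

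The SAP also plans corrected versions. DN_Cmax "will additionally be calculated for the estimated rhu-pGSN profile for both the change from pre-dose day 1 and the double-delta method". DN_AUC0-t and DN_AUC0-8 each "will additionally be calculated for the estimated rhu-pGSN profile for both the change from pre-dose on each study day and the double-delta method". SAP 9.2 repeats this for the change-from-pre-dose profile ("The following parameters (including dose normalized parameters) will be calculated for each study day") and names AUC0-t, AUC0-8h and Cmax. The double-delta subsection has the same list, and Tables 14.2.3.1-14.2.3.3 are reserved for the results. DN_AUC0-inf has no such sentence in its row and is not on either list.

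Protocol 4.3 gives the background in health: "At normal levels of 200-300 mg/L, it is the fourth most abundant protein in the circulation". It adds that levels drop in several acute conditions, but gives no level for CAP.

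**The concern.** A dose-normalised parameter is normally read across dose groups: a flat pattern suggests proportional exposure, and a falling one suggests less than proportional exposure. Dividing a total that contains a background unrelated to dose builds a fall into the numbers. The background contributes its own size divided by dose, which is four times as large at 6 mg/kg as at 24 mg/kg.

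The report will then show two sets of dose-normalised values that point in different directions, and the SAP does not say which one bears on proportionality. The total-pGSN set comes first in the table order and is the one summarised with geometric means and geometric CVs. The shells for the corrected set have neither. For DN_AUC0-inf the reader has only the version that contains the background. What is at stake is the description of rhu-pGSN exposure across doses, which belongs to the protocol's secondary PK endpoint.

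**Working it through.** The documents state no figure for dose-normalised exposure, so there is nothing to reproduce. The check is algebra followed by an illustration.

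**Inputs from the documents.** Doses D of 6, 12 and 24 mg/kg (SAP 2.1). Normal endogenous level of 200-300 mg/L (Protocol 4.3). Sampling at pre-dose, 5-10 minutes, and 2, 8, 12 and/or 16, and 24 hours (SAP 9). Log-down, linear-up trapezoid (SAP 9.1).

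**Assumptions not in the documents.** Background B of 50-300 mg/L, widened downwards because no CAP level is given. B is constant over 24 hours and unaffected by dose. One-compartment bolus kinetics, with volume V of 0.04-0.10 L/kg and a half-life of 20 h (k = ln 2/20 = 0.0347 per hour).

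**Algebra.** With exactly linear rhu-pGSN kinetics:

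- Cmax(total)/D = B/D + 1/V
- AUC0-T(total)/D = B×T/D + (1 − exp(−kT))/(kV)

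In each line the second term does not depend on dose and the first falls as 1/D. Any B above zero therefore produces a decline. Subtracting the Day 1 pre-dose value removes B and leaves only the constant term.

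**Ends of the DN_Cmax range, 24:6 ratio.**

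- B = 50, V = 0.04: [(50 + 600)/24] / [(50 + 150)/6] = 27.08/33.33 = 0.81
- B = 300, V = 0.10: [(300 + 240)/24] / [(300 + 60)/6] = 22.5/60 = 0.375

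Within the protocol's normal range alone, the upper end is at B = 200, V = 0.04: [(200 + 600)/24] / [(200 + 150)/6] = 33.33/58.33 = 0.57.

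**Worked case, Day 1, B = 250 mg/L, V = 0.05 L/kg.** SAP sampling times and trapezoid, with the first post-dose sample at 0.125 h and both the 12- and 16-hour samples used:

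| Parameter | 6 mg/kg | 12 mg/kg | 24 mg/kg | 24:6 |
|---|---|---|---|---|
| DN_Cmax, total | 61.6 | 40.7 | 30.3 | 0.49 |
| DN_AUC0-8, total | 472.1 | 305.4 | 222.0 | 0.47 |
| DN_AUC0-t (24 h), total | 1325.5 | 825.3 | 575.1 | 0.43 |
| DN_AUC0-inf, total | 8462.2 | 3347.1 | 1668.5 | 0.20 |
| DN_Cmax, change from pre-dose | 19.9 | 19.9 | 19.9 | 1.00 |
| DN_AUC0-8, change from pre-dose | 138.5 | 138.5 | 138.5 | 1.00 |
| DN_AUC0-t, change from pre-dose | 324.6 | 324.6 | 324.6 | 1.00 |

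DN_AUC0-inf is distorted most because its extrapolation uses a terminal slope fitted to the total. That slope flattens towards the background: the apparent half-life is 98, 59 and 40 h at the three doses, against a true 20 h.

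**Range over B 50-300 mg/L and V 0.04-0.10 L/kg, half-life 20 h, 24:6 ratio.** DN_Cmax 0.38-0.81; DN_AUC0-8 0.36-0.79; DN_AUC0-t 0.34-0.75; DN_AUC0-inf 0.12-0.59. The change-from-pre-dose versions of the first three are 1.00 throughout. The AUC ratios also depend on half-life. With half-lives of 8-24 h and B of 100-300 mg/L, they run 0.34-0.68 to 8 hours and 0.31-0.64 to 24 hours.

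**The DN_AUC0-8 row.** SAP 9.1 defines it as AUC0-24 divided by dose, whereas the SAP abbreviation list uses AUC0-8. Read literally, the Section 9.1 row takes the 24-hour ratios and largely duplicates DN_AUC0-t.

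**The case against.** The strongest reply is that the SAP has already dealt with this for three of the four parameters. The rows that define DN_Cmax, DN_AUC0-t and DN_AUC0-8 on the total also call for two baseline-corrected versions, and dedicated tables report them. Total pGSN and estimated rhu-pGSN are separately defined and separately titled, so different values for the two are expected and are not in themselves a contradiction. The PK objective is to characterise the profile, all PK output is descriptive, and no proportionality model or test is specified.

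Most of this stands. A reader might infer that the plan has no valid dose-normalised exposure, or will necessarily conclude that exposure is less than proportional. The documents do not support that, because the corrected set is planned and does not fall under proportional kinetics. A reader might also infer that escalation or the next-phase dose would be misled. Escalation rests on review of safety through Day 7, and no passage ties the recommended-dose objective to a dose-normalised parameter.

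The size is also assumption-bound. Volume, half-life and the CAP background are not in the documents, and neither is independence of the background from dose, although subtracting the placebo mean in the double-delta method relies on a similar premise.

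The reply does not cover two things: the SAP is silent on which set is the basis for proportionality, and DN_AUC0-inf has no corrected version at all.

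**Conclusion.** The point holds as a defect of specification and presentation. Four dose-normalised parameters of total pGSN are planned that cannot be read for proportionality. The direction of the distortion follows from the algebra for any background above zero that does not depend on dose. The size is illustrative: a DN_Cmax ratio of about 0.38-0.81 instead of 1.00 over the assumed background and volume, and 0.38-0.57 if the background stays within the protocol's normal range.

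For DN_Cmax, DN_AUC0-t and DN_AUC0-8 the remedy already exists in Tables 14.2.3.x and needs only to be named as the basis. For DN_AUC0-inf there is none. With no formal test planned, the harm is confined to descriptive interpretation of PK across doses. It is worth correcting, but it does not threaten the trial's safety conclusions.

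**What to change.** 1. Remove the total-pGSN dose-normalised parameters from SAP 9.1, Tables 14.2.2.1-14.2.2.3 and Listings 16.2.6.3.x. Alternatively, keep them with a footnote that they contain endogenous protein and are not interpretable for dose-proportionality.
2. State in SAP 9.2 that the Day 1 baseline-corrected DN_Cmax, DN_AUC0-t and DN_AUC0-8 are the only basis for any proportionality statement. Day 1 is the cleanest choice, because its pre-dose sample contains no study drug. It also avoids the mismatch between the DN_Cmax row, which corrects to the Day 1 pre-dose value, and the other rows, which correct to each day's own.
3. Either compute AUC0-inf and DN_AUC0-inf on the corrected profile or drop DN_AUC0-inf. SAP 9.2 notes that corrected concentrations can be zero or negative, so a log-linear terminal slope may not be estimable in every subject. The SAP should say how such subjects are handled.
4. Correct the DN_AUC0-8 row in SAP 9.1 so that it uses AUC0-8, in line with the abbreviation list.

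The cost is minor edits to the SAP and shells, with no new data. Nothing is lost for the three parameters that already have corrected versions. DN_AUC0-inf is lost if it is not recomputed on the corrected profile.
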